4.4.2 Laboratory safety measurements and variables

4.4.2.1 Methods of assessment

An extended laboratory screen with blood and urine sampling for determination of clinical chemistry, haematology and urinalysis parameters will be taken at the enrolment visit (visit 1) and at the follow-up visit (visit 6). If a patient needs an early discontinuation visit, an extended laboratory screen (including a urine pregnancy test) should be done. If a patient needs an unscheduled visit, an extended laboratory screen (except a urine pregnancy test) could be done.

A laboratory screen with blood and urine sampling for determination of clinical chemistry, haematology and urinalysis parameters will be taken at visit 2, visit 4 and visit 5. The laboratory samples will be analysed at a central laboratory, Quintiles Laboratories (QLABS), Ltd., Smyrna, Georgia, USA, except for the urine pregnancy test, which will be done by dipstick at the study site and entered into the Pregnancy Test (PREG) module of the eCRF. See [Table 7](#) for the total volume of blood that will be drawn from the patients throughout the conduct of the study.

A urine pregnancy test for women of childbearing potential only will be conducted at visit 1, visit 2, visit 6 and early discontinuation visits.

Table 6 Summary of the laboratory safety variables analysed in the study

Clinical chemistry	Haematology
S-Aspartate transaminase (AST)	B-Haemoglobin
S-Alanine transaminase (ALT)	B-Red blood cell (RBC) count
S-Alkaline phosphatase	B-White blood cell (WBC) count
S-Total bilirubin	B-Platelet count
S-Creatinine	B-Reticulocyte count
S-Thyroid stimulating hormone (TSH) ^a	B-WBC differential count
S- Free Thyroxine (free T4) ^a	B-Mean corpuscular volume (MCV)
S-Blood urea nitrogen (BUN)/urea	B-Mean corpuscular haemoglobin concentration (MCHC)
S-Albumin	
S-Sodium	Urinalysis (dipstick)
S-Potassium	U-Protein
S-Magnesium	U-Glucose
S-Calcium	U-Blood
S-Creatine phosphokinase (CPK)	Urine pregnancy test ^b (dipstick)
P-Non-fasting plasma glucose	
High-sensitivity C-reactive protein (hs-CRP)	
B-Haptoglobin	
Helicobacter Pylori (H pylori), antibody immunoglobulin G [IgG] test ^c	

^a Conducted at visit 1, visit 6 and early discontinuation visits.

^b Conducted at visit 1, visit 2, visit 6 and early discontinuation visits only for women of childbearing potential.

^c Conducted at visit 1 only.

Laboratory values outside the reference ranges suspected to be of any clinical significance could be re-checked during an unscheduled visit. Randomised patients who develop clinically significant abnormal laboratory values must be followed until normalisation or for as long as the investigator considers necessary.

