2.2 Additional Objectives

- To assess the safety and tolerability during 4 weeks treatment with AZD3355 65 mg bid as add-on treatment to a PPI in partial responders to PPI treatment who still experience GERD symptoms

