All patient-reported data will be collected via electronic devices. An e-diary device will be used for the twice daily symptom registration and will be brought home by the patients. A similar electronic device will be used at the clinic for completion of the additional PRO instruments at each visit. SAEs will be collected during the entire study period and AEs will be collected and followed up after randomisation (see section 4.4.1.1). Concomitant medication will be monitored at all visits.

Part 1

Visit 1: (12 to 8 days prior to randomisation) After giving written informed consent, patients will receive training in how to complete PRO instruments and use the site-based electronic device. Thereafter, they will complete the modified RDQ screening instrument. If the patient fulfils the inclusion criteria of the modified RDQ, additional PRO instruments (see Table 3) will be completed prior to any further assessment.

Each patient will then undergo a physical examination, an extended laboratory screen, ECG, supine BP and pulse, medical and surgical history, weight and height, and will be evaluated for all inclusion and exclusion criteria. Women of childbearing potential will undergo a urine pregnancy test.

Patients will receive training in how to use the e-diary device, and will start recording in the e-diary in the evening on the day of visit 1. They will also receive a selected over-the-counter (OTC) antacid as rescue medication (GELUSIL[®] antacid/anti-gas tablets) to use as needed if they experience GERD symptoms during the study. The patients will be instructed to bring any empty GELUSIL[®] antacid/anti-gas tablets cartons and/or blister packs, as well as any unused rescue medication, with them to visit 2.

Patients from selected sites, who consent to participate in the cognitive interviews, will be scheduled for the first cognitive interview (at visit 2 with a time window of up to 5 days prior to visit 2) and the second cognitive interview (at visit 5 with a time window of up to 7 days prior to or 2 days after visit 5).

ePRO data collection during Part 1

During Part 1, patients will enter twice daily e-diary recordings of GERD symptoms, impact of symptoms and the use of GELUSIL[®] antacid/anti-gas tablets. Throughout the study, the study staff will monitor the e-diary compliance and call each non-compliant patient in order to support and resolve possible issues.

Part 2

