Randomised patients will continue twice daily e-diary recordings of GERD symptoms, impact of symptoms and use of GELUSIL[®] antacid/anti-gas tablets until the morning on the day of visit 5. The study staff will continue the regularly monitoring of the e-diary compliance as during Part 1.

Visit 3 (phone visit). 5 to 9 days after randomisation, the study staff at the clinic will phone the patient, ask about drug compliance and discuss the e-diary device and e-diary compliance.

Visit 4. 12 to 16 days after randomisation, patients should complete additional PRO instruments prior to any further assessment (see [Table 1](#)), dECG, supine and standing BP and pulse, laboratory screen, e-diary device check and e-diary compliance review and drug accountability. Drug will be dispensed for the last two treatment weeks. A second carton of rescue medication (GELUSIL[®] antacid/anti-gas tablets) will be dispensed for continued use as necessary.

The patients will also be instructed to bring any empty bottles, cartons and/or blister packs, as well as any unused investigational products and rescue medication, with them to visit 5.

Visit 5. 26 to 30 days after randomisation, patients should complete additional PRO instruments (see [Table 3](#)) prior to any further assessment, physical examination, weight, dECG, supine and standing BP and pulse, laboratory screen, e-diary device check and e-diary compliance review and drug accountability. The patient will take the last dose of study drug the evening before the day of visit 5, the optimised PPI treatment will continue. The e-diary recordings of symptoms will end in the morning the day of visit 5 and the e-diary device will be collected at the site.

The patients will be instructed to bring any empty GELUSIL[®] antacid/anti-gas tablets cartons and/or blister packs, as well as any unused rescue medication, with them to visit 6.

If scheduled, the second cognitive interview will be performed at visit 5 (with a time window of up to 7 days prior to or 2 days after visit 5). When an interview is conducted on the day of visit 5, then the interview will be carried out after the completion of the PRO instruments, and prior to clinical assessments.

Visit 6. 12-16 days after visit 5, a follow up visit is done. Each patient will undergo a physical examination, an extended laboratory screen, dECG, supine and standing BP and pulse. Women of childbearing potential will undergo a urine pregnancy test.

Figure 2 Study flow chart

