3.3.6.3 Procedures for early discontinuation after randomisation

Patients who discontinue after randomisation should always be asked about the reason(s) for their early discontinuation and the presence of any AEs. All patients should be seen and assessed by an investigator. For early discontinuation visits, assessments according to end-of-treatment visit (visit 5) should be done, including patients completing the visit 5 ePRO assessments. In addition, a dECG, an extended laboratory screen and a urine pregnancy test for women of childbearing potential, should be performed. All patients should be strongly encouraged to attend the follow-up visit. AEs and/or SAEs, including QTcF prolongations, must be followed up. The e-diary device and investigational product must be returned by the patient, drug accountability, and an e-diary device check must be done. Patients withdrawn from the investigational product due to daily paresthesiae for at least 7 consecutive days must be referred to a board certified neurologist for examination and followed-up by the investigator 12-16 days after discontinuation of investigational product (visit 6). A copy of the report from the neurologist must be provided to AstraZeneca.

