4.5 Volume of blood sampling and handling of biological samples

The total volume of blood that will be drawn from each patient in this study is as follows:

Table 7 Volume of blood to be drawn from each patient

Assessment		Sample volume (mL)	No. of samples	Total volume (mL)
Safety	Clinical chemistry	12.5 mL (extended lab screen)	2 (visits 1 and 6/early discount)	25.0 mL
		9.0 mL	3 (visits 2, 4 and 5)	27.0 mL
	Haematology	3.0 mL (extended lab screen)	2 (visits 1 and 6/early discount)	6.0 mL
		3.0 mL	3 (visits 2, 4 and 5)	9.0 mL
Total				67.0 mL

However, if additional tests are required for the patient's safety ie unscheduled visits, retests etc, the volume of blood might be increased.

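### Completers have no scheduled on-treatment TSH or free T4, so the schedule cannot systematically detect a thyroid effect that reverses once AZD3355 is stopped

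*Protocol*

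**What the plan says.** Protocol section 2.2 states the safety objective as follows: "To assess the safety and tolerability during 4 weeks treatment with AZD3355 65 mg bid as add-on treatment to a PPI". Table 5 names laboratory variables among the means of addressing it.

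Section 4.4.2.1 has two laboratory panels. The extended screen is taken at visits 1 and 6. The ordinary screen "will be taken at visit 2, visit 4 and visit 5". Table 6 lists TSH and free T4 under clinical chemistry, and footnote a limits them: "Conducted at visit 1, visit 6 and early discontinuation visits". Two further routes to an extended screen exist:

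- For a patient who stops after randomisation, section 3.3.6.3 says that "a dECG, an extended laboratory screen and a urine pregnancy test for women of childbearing potential, should be performed".
- Section 4.4.2.1 adds: "If a patient needs an unscheduled visit, an extended laboratory screen (except a urine pregnancy test) could be done".

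On timing, section 3.1 places visit 1 "12 to 8 days prior to randomisation" and visit 5 at 26 to 30 days after randomisation. The last dose is the evening before visit 5. Of visit 6 it says: "12-16 days after visit 5, a follow up visit is done".

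**The concern.** The objective concerns the treatment period, but for completers both scheduled thyroid samples lie outside it. TSH and free T4 are the only chemistry variables that Table 6 schedules again after baseline but keeps out of visits 2, 4 and 5. The only other footnoted chemistry test, *H. pylori* serology, is done at visit 1 alone and serves as a baseline characteristic.

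If the drug shifted thyroid hormones only while it was being taken, the shift could fade before visit 6 and go unrecorded in completers, the patients with the longest exposure. Section 4.4.2.1 requires clinically significant abnormal values in randomised patients to be followed up, but that safeguard works only for abnormalities that a sample has picked up.

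The protocol also treats the two groups differently at the same milestone. A patient who stops early has thyroid function tested at the discontinuation visit. A patient who reaches the planned end of treatment does not have it tested at visit 5.

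**Working it through.** **1. The plan's own total.** Table 7 is the only figure tied to this schedule. It gives 12.5 mL of chemistry blood for an extended screen, with the count entered as "2 (visits 1 and 6/early discount"; 9.0 mL for each of three ordinary screens; and 3.0 mL of haematology at all five visits.

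2 × 12.5 + 3 × 9.0 + 2 × 3.0 + 3 × 3.0 = 25.0 + 27.0 + 6.0 + 9.0 = 67.0 mL. This matches the stated total.

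**2. Consistency.** Four places were compared.

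| Place | Extended screen (with TSH, free T4) | Ordinary screen |
|---|---|---|
| Section 4.4.2.1 text | Visits 1 and 6, early discontinuation; optional at unscheduled visits | Visits 2, 4, 5 |
| Table 1, footnotes a and f | Visits 1 and 6, early discontinuation | Visits 2, 4, 5 |
| Table 6, footnote a | Visits 1 and 6, early discontinuation | – |
| Table 7 | Visits 1 and 6 or early discontinuation | Visits 2, 4, 5 |

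They agree. The point is a limit of a consistent schedule, not a contradiction.

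**3. Timing for a completer.** The inputs are the visit windows and the last-dose rule in section 3.1.

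- First thyroid sample: 8 to 12 days before randomisation. The first dose is given at visit 2, so this is before treatment.
- Second thyroid sample, in days after randomisation: 26 + 12 = 38 at the earliest, 30 + 16 = 46 at the latest.
- Interval between the two samples: 8 + 38 = 46 to 12 + 46 = 58 days.
- Calendar days from the day of the last dose to visit 6: 12 + 1 = 13 to 16 + 1 = 17.
- Scheduled thyroid samples between first and last dose: 0.

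**4. Blood volume if visit 5 is added.** An extended chemistry sample exceeds an ordinary one by 12.5 − 9.0 = 3.5 mL. With the full extended volume at visit 5, the total is 67.0 + 3.5 = 70.5 mL. Table 7 does not split the 3.5 mL by test, so this is an upper figure for adding the two thyroid tests alone.

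**The case against.** The strongest reply is that sampling at baseline and at safety follow-up is a deliberate choice, applied consistently. The follow-up period is described as being for safety assessment. Safety is an additional objective in a study built to validate questionnaires. The concerns named in section 3.2.2 are paresthesiae, QTc and haemodynamic effects, and ECG, blood pressure and pulse are measured during treatment. Under section 4.4.3.1 the thyroid is part of the physical examination at visits 1, 2, 5 and 6. All of this stands and limits the weight of the point. An examination does not replace biochemistry, however, and visit 6 cannot show what has already reversed.

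Four stronger readings are tempting, and the documents do not support them.

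- *No completer can have an on-treatment value.* An extended screen may be done at an unscheduled visit. That route is optional and driven by need, so it gives no systematic comparison, but it exists. The accurate statement is that no such value is scheduled.
- *The safety objective cannot be met.* Table 5 addresses it through several kinds of data together. The randomised comparison at visit 6 can still show persistent thyroid effects, and early discontinuers add values from their discontinuation visit, though they are a selected group.
- *The comparison between arms is confounded by dropout.* That would require discontinuation and visit 6 values to be pooled. The protocol specifies no such analysis, and summaries of laboratory data are normally left to the SAP, which is not shown. Discontinuers are also strongly encouraged to attend visit 6, so those who do attend have a value comparable with completers'.
- *A given share of the effect is lost by visit 6.* Any such share needs an assumed rate of reversal. The protocol gives none.

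**Conclusion.** The point holds as a limitation of the sampling schedule. Completers have 0 scheduled TSH or free T4 values between first and last dose, and their only scheduled post-baseline value comes 13 to 17 calendar days after the day of the last dose. The design can detect a thyroid change that persists off drug. It has no systematic means of detecting one that reverses.

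This rests only on the visit windows, the last-dose rule and Table 6 footnote a; no assumption about thyroid physiology is needed. The consequence is conditional: it matters only if a reversible effect exists. The documents report no thyroid signal, and the size of any missed effect cannot be derived from them. The case for changing the schedule is the poor fit with the stated objective and the low cost of closing the gap, not evidence of harm.

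**What to change.** Add TSH and free T4 to the chemistry sample already drawn at visit 5, and keep them at visit 6. Amend together section 3.1 (visit 5), the section 4.4.2.1 text, Table 1, Table 6 footnote a and Table 7, so that the places which now agree still agree.

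Summarise visit 5 and early-discontinuation values as end-of-treatment values, separately from visit 6 follow-up values. This puts completers and early stoppers at the same milestone and avoids mixing samples taken at different times after the last dose.

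Moving the second extended sample from visit 6 to visit 5 would leave the volume at 67.0 mL (2 × 12.5 + 3 × 9.0 + 5 × 3.0), but it would give up the routine off-drug value and so open a different gap. Adding is preferable to swapping.

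The cost is one more assay of each thyroid test per completer and up to 3.5 mL more blood, for a total of at most 70.5 mL. No extra visit or venepuncture is needed.

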4.4.2.2 Derivation or calculation of outcome variables

See section 4.4.1.2 for how an AE based on laboratory values will be recorded and reported.

4.4.3 Vital signs, ECG and physical examination

4.4.3.1 Methods of assessment

Physical examination (ie, general appearance, skin, head and neck, lymph nodes, thyroid, musculoskeletal/extremities, cardiovascular, lungs, abdomen and neurology, including cranial nerve functions) will be done at visit 1, visit 2, visit 5 and visit 6. dECG will be recorded at all visits at the study site (at visit 2, prior to and 1 hour after the first dose of investigational product) including at the early discontinuation visit. Supine pulse and BP will be obtained at the study site at visit 1, supine and standing pulse and BP will be obtained at the study site at visit 2, 4, 5 and 6 and at the early discontinuation visit if applicable. At visit 2 the supine and standing pulse and BP will be obtained after the dECG recordings prior to and 1 hour after the first dose of investigational product.

At visit 2, 4, 5 and 6 dECG will be performed after the PRO assessments and cognitive interviews are completed (if applicable).

ECG

eResearch Technology (eRT), Inc. (Philadelphia, Pennsylvania) will provide the equipment and review of dECGs. The dECGs will be acquired utilizing the Mortara ELI 150, a Transtelephonic Modem-Based 12-Lead ECG Delivery.

After the patient has been supine for at least 10 minutes, three standard 12-lead digital ECG recordings (triplicate) will be performed within a 5-minute period while the patient remains supine. Printouts of the dECG (paper speed 25mm/sec) will be obtained for review by the investigator. ECGs will be evaluated as either "Normal" or "Abnormal" with special attention to QTcF and recorded in the eCRF. If an ECG is evaluated as "Abnormal", the specific abnormality and investigator judgement regarding clinical significance is required.

All dECGs will be reviewed by a trained eRT Cardiac Safety Specialist for correct lead and beat selection and caliper. Each dECG will be submitted to a Cardiologist through eRT for clinical evaluation and verification of the caliper placement. A final report from each dECG will be delivered by eRT to the investigator within 72 hours.

At visit 2 the ECG electrodes should remain on the patient to ensure that the same position is used for the dECG recordings before and after the first dose of IP.

Pulse and BP

Supine BP and pulse will be measured in all patients at visit 1 immediately following the dECG recording and before blood samples are obtained.

Supine and standing BP and pulse will be measured in all patients at visit 2, 4, 5, 6 and at the early discontinuation visit immediately following the dECG recordings and before blood samples are obtained.

The following procedure should be applied for each measurement: After the supine BP and pulse have been measured, the patient will be instructed to stand with arms relaxed at their sides. BP and pulse will then be measured after 1 minute in the upright position.

4.5 Volume of blood sampling and handling of biological samples

The total volume of blood that will be drawn from each patient in this study is as follows:

Table 7 Volume of blood to be drawn from each patient

Assessment		Sample volume (mL)	No. of samples	Total volume (mL)
Safety	Clinical chemistry	12.5 mL (extended lab screen)	2 (visits 1 and 6/early discount)	25.0 mL
		9.0 mL	3 (visits 2, 4 and 5)	27.0 mL
	Haematology	3.0 mL (extended lab screen)	2 (visits 1 and 6/early discount)	6.0 mL
		3.0 mL	3 (visits 2, 4 and 5)	9.0 mL
Total				67.0 mL

However, if additional tests are required for the patient's safety ie unscheduled visits, retests etc, the volume of blood might be increased.

4.5.1 Analysis of biological samples

4.5.1.1 Clinical chemistry samples

The analyse stability limits defined by the central laboratory, QLABS, will be applied to all analyses performed on behalf of AstraZeneca. QLABS will not analyse samples that fall outside these stability limits. Analytical data will not be reported if found to have been derived from a sample that fell outside these stability limits. The standards of procedure followed by QLABS may be amended in accordance with its Standard Operating Procedures.

If QLABS chooses to sub-contract the analytical work to another laboratory, QLABS must assure itself and provide assurance to AstraZeneca that the other laboratory will apply defined stability limits to all analyses performed on behalf of AstraZeneca. Samples falling outside these limits must not be analysed or data reported.

5. DATA MANAGEMENT

The patients will use electronic devices for collection of the PRO data (see section 4.3) and trained study personnel at the study site will be responsible for entering the patient identifier data and visit data in the site-based electronic device and e-diary device (see section 8.4). The ePRO system will be provided by invivodata, Pittsburgh, Pennsylvania, USA. The ePRO data will be transferred either via telephone modems or wireless data transfers to a central database.

The ePRO system is a specialised data capture appliance designed for entry of data in a way that is attributable, secure and accurate in compliance with FDA's Final Rule: Electronic Records; Electronic Signature (21 CFR Part 11).

After the ePRO data have been transferred to the central database, it can be reviewed via a secure access to a web-server. All data will be time stamped and changes on the visit and identifier data will be tracked in the systems audit trail. Each user needs to have system training before any access will be given out. All actions on data are to be accomplished using the system controls compliant with 21 CFR part 11 that are built in to the system application used to collect, clean, review and archive clinical study data.

The clinical data will be entered into COOL, the web based data entry system, at the study site. Trained study personnel will be responsible for entering data on the observations, tests and assessments specified in the protocol into the COOL system and according to the eCRF Instructions.

The eCRF Instructions will also provide the study site with data entry instructions. Data entered in the COOL system will be immediately saved to a central database and changes tracked to provide an audit trail. When data have been entered reviewed, edited and Source Data Verification (SDV) performed the principal investigator will be notified to sign the eCRF electronically as per the agreed project process and data will be locked to prevent further editing. A CD/DVD containing a copy of eCRF data will be distributed to the study sites for archiving in the ISF.

All coding will be done in accordance with AstraZeneca standard procedures, and continually throughout the study. Queries can be raised by the coding expert at any time during the study period and the query tool in COOL will be used.

AE, diagnosis from medical history and procedures from surgical history will be classified according to the terminology of the Medical Dictionary for Regulatory Activities (MedDRA, latest version throughout the study). "The Lowest Level Term" that best reflect the term used by the investigator will be chosen when classifying the terms and "Preferred Terms" will be used mainly for output (data presentation) for the grouping of terms. Concomitant medication will be classified according to the AstraZeneca Drug Dictionary (AZDD), the Anatomical Therapeutic Chemical (ATC) system and the Committee for Medicinal Products for Human Use (CHMP) route of administration dictionary.

Laboratory data will be delivered to AstraZeneca R&D Mölndal, Sweden, by the central laboratory. The laboratory data will be loaded into the study database.

A central ECG vendor will be used to collect dECG data. Sites will transmit the dECG data to the vendor's central database using equipment provided by the vendor. The vendor will identify, examine and analyse the data and will send the ECG report to site.

Online study reports will be accessible to the study team during the study. The source files will be returned to AstraZeneca R&R, Mölndal.

